10.2.3.3 Final PFS Analysis and Interim OS analysis

The final PFS analysis will be performed when at least 210 progression or death events are observed.

The PFS assessed by the Independent Review Committee (IRC) will be used for the primary analysis, while the Investigator assessment will be used for the secondary analysis of PFS.

The unstratified log rank test will be used to compare the PFS of Arm A and Arm B.

Secondary time-to-event endpoints (DR, OS) will be analyzed according to the Kaplan-Meier method and compared between treatment groups using the log-rank test. A stratified log-rank test for the main endpoint (PFS) will be performed as supportive analysis. Both the IRC and Investigator's assessments will be used.

Counts and percentages, with their corresponding exact 95% confidence intervals, will be calculated for the RR (IMWG criteria and, separately, minor response). The Fisher's exact test will be used to compare the response rates of the Arm A and B.

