4.1 Analysis sets definitions

“All Randomized Patients” analysis set is defined as all patients who are randomized to either treatment arm, independent of whether they received the study drug.

“All Treated Patients” analysis set is defined as all randomized patients who receive at least part of one dose or infusion of the investigational agents.

“All Evaluable Patients” analysis set is defined as all randomized patients who have completed at least one full cycle of treatment or have received two incomplete cycles followed by at least one response assessment not less than eight weeks (\pm one week) after treatment onset. Patients withdrawn from the study due to early disease progression or treatment-related toxicity will be considered as “early progression” or “treatment failure”, respectively, even though they have not received a full cycle. Patients withdrawn due to significant clinical deterioration of unknown reason, hypersensitivity reactions, or refusal to continue on study for any reason or unrelated AEs without any disease assessments after the start of study treatment or those patients with a protocol deviation resulting in an impossibility of drawing conclusions about the efficacy of the study therapy will be considered not evaluable for efficacy and their response will be categorized as “non evaluable”.

“All Responder Patients” analysis set is defined as all evaluable patients who have minor response or better as overall best response.

“All Crossover Patients” analysis set is defined as all patients randomized to Arm B who have documented disease progression after their eighth week from randomization and cross over to Arm A.

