4.2 Efficacy populations

The “All Randomized Patients” analysis set will be used for the primary endpoint analysis of Progression-free survival (PFS) and the main efficacy analysis, as well as for all OS analyses.

For futility analysis based on objective response rate, the “All Evaluable Patients” analysis set will be used.

The “All Randomized Patients” and “All Evaluable Patients” datasets will be used for the final analysis of RR.

The “All Responder Patients” dataset will be used for the duration of response (DR) calculation.

[figure not shown]
The “All Crossover Patients” dataset will be used for the exploratory inpatient comparison of response and PFS (before and after crossover).

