The following time-dependent covariates will be included in the IPCW analysis: ECOG, Body Surface Area (BSA), m-protein value (serum/urine), number of adverse events grade \geq 3, bone marrow plasma cells, creatinine, LDH, hemoglobin and corrected serum calcium. Also, baseline covariates such as gender, age, MM type (i.e.: IgG, IgA, light chain myeloma, non-secretory), number of prior lines of anticancer treatment, status (relapsed vs. relapsed/refractory), refractory status to bortezomib, lenalidomide/thalidomide prior therapy, refractory status to last prior therapy, refractory status to IMiD therapy, refractory status to PIs therapy, genetic risk, previous SCT, time from diagnosis to randomization, time from last progression before randomization, International Staging System, Durie-Salmon stage, presence of plasmacytomas, presence of lytic lesions, number of plasmacytomas, sum of the dimensions of plasmacytomas, will be included.

The reasons for censoring of OS will be shown using counts and percentages.

An analysis will be carried out in the subpopulation of patients without crossover or subsequent therapy in order to investigate the isolated effect of study treatments in survival in this subpopulation. It will be also carried out in the subpopulation of patients without crossover or subsequent therapy and with event in the primary analysis of PFS by IRC.

Response rate:

Binomial estimates with exact 95% CIs will be calculated for the analysis of response rate. Randomized patients not evaluable for response will be excluded from the denominator exclusively for the futility analysis, but will be included in all the final efficacy analyses. A supportive analysis will be also done in the “All Evaluable Patients” population.

The magnitude of response, in patients with secretory MM, will be described by waterfall plots showing the best M-spike reduction from baseline.

A supportive analysis of response rate will be performed taking into account PR or better as best overall response based on the IMWG criteria.

Duration of response:

Duration of objective response will be analyzed according to the Kaplan-Meier method and compared between treatment groups using the log-rank test.

DR requiring confirmation of PD for determination of PFS will be analyzed according to the Kaplan-Meier method and compared between treatment groups using the log-rank test.

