DR for patients who have PR or better as best overall response based on the IMWG criteria will be calculated as a supportive analysis.

Time to response:

Time to response will be analyzed according to the Kaplan-Meier method and compared between treatment groups using the log-rank test.

Time to response for patients who have PR or better as best overall response based on the IMWG criteria will be also calculated as a supportive analysis.

Analysis of crossover:

Descriptive frequency tables with the number of patients who switch from Arm B to Arm A after disease progression will be calculated.

Exploratory intrapatient comparison of response and PFS (before and after crossover) will be performed for patients who switch from Arm B to Arm A after disease progression.

The patients within the “All Crossover Patients” dataset will be listed with the cycle when the crossover occurs, and the response and PFS before and after crossover.

A comparison of the baseline characteristics in patients with Crossover *vs.* No crossover will be done to rule out that patients with crossover can have a better prognosis than patients without crossover. For two-stage method a logistic stepwise regression and the comparison of PFS between patients with crossover versus patients with no crossover is performed to check the assumption of no ‘unmeasured confounders’. Post-progression survival data is adjusted by a Weibull parametric accelerated failure time model.

A listing of patients with crossover will be provided in order to confirm if PD was seen before crossover and if this PD was confirmed.

Statistics of the time (in months) from study initiation to crossover will also be included.

Analysis of prognostic factors, subgroup analysis and multivariate analyses:

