11.3.4.4 Duration of response

Table 11.3.4.4.1 DR (Independent Review assessment and “All Responder Patients” population)

	Arm A	Arm B	Parameter	p-value
N				
Events				
Censored				
Median DR			Log-Rank: HR (95% CI) :	LR: HR:
DR at 6 months			Diff:	

Kaplan-Meier plot will be also shown (Figure 11.3.4.4.1)

Table 11.3.4.4.2 DR (Investigator assessment and “All Responder Patients” population)

	Arm A	Arm B	Parameter	p-value
N				
Events				
Censored				
Median DR			Log-Rank: HR (95% CI) :	LR: HR:
DR at 6 months			Diff:	

Kaplan-Meier plot will be also shown (Figure 11.3.4.4.2)

Table 11.3.4.4.3 DR without MR (Independent Review assessment and “All Responder Patients” population)

	Arm A	Arm B	Parameter	p-value
N				
Events				
Censored				
Median DR			Log-Rank: HR (95% CI) :	LR: HR:
DR at 6 months			Diff:	

Kaplan-Meier plot will be also shown (Figure 11.3.4.4.3)

Table 11.3.4.4.4 DR without MR (Investigator assessment and “All Responder Patients” population)

	Arm A	Arm B	Parameter	p-value
N				
Events				
Censored				
Median DR			Log-Rank: HR (95% CI) :	LR: HR:
DR at 6 months			Diff:	

Kaplan-Meier plot will be also shown (Figure 11.3.4.4.4)

Table 11.3.4.4.5 DR with PD confirmation (Independent Review assessment and “All Responder Patients” population)

	Arm A	Arm B	Parameter	p-value
N				
Events				
Censored				
Median DR			Log-Rank: HR (95% CI) :	LR: HR:
DR at 6 months			Diff:	

Kaplan-Meier plot will be also shown (Figure 11.3.4.4.5)

Table 11.3.4.4.6 DR with PD confirmation (Investigator assessment and “All Responder Patients” population)

	Arm A	Arm B	Parameter	p-value
N				
Events				
Censored				
Median DR			Log-Rank: HR (95% CI) :	LR: HR:
DR at 6 months			Diff:	

Kaplan-Meier plot will be also shown (Figure 11.3.4.4.6)

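### Duration of response is compared between arms by log-rank and hazard ratio in responders only, which is not a randomized comparison and cannot be read as the drug's effect on durability

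*SAP*

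**What the plan says.** SAP 4.1 defines the responder set by outcome: the All Responder Patients "analysis set is defined as all evaluable patients who have minor response or better as overall best response". SAP 4.2 assigns that set to this endpoint: it is the one whose "dataset will be used for the duration of response (DR) calculation". SAP 6.1.2 starts the clock at the first documented response, not at randomization.

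SAP 6.2.3 then compares the arms: "Duration of objective response will be analyzed according to the Kaplan-Meier method and compared between treatment groups using the log-rank test". Protocol 10.2.3.3 handles duration of response (DR) in the same sentence as overall survival: "Secondary time-to-event endpoints (DR, OS) will be analyzed according to the Kaplan-Meier method and compared between treatment groups using the log-rank test".

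The shells in SAP 11.3.4.4, from "Table 11.3.4.4.1 DR (Independent Review assessment and" onward to Table 11.3.4.4.6, show DR by arm for independent review and investigator assessment, with and without minor response, and with confirmed progression. Each prints a log-rank p-value, a hazard ratio with 95% CI and p-value, and a between-arm difference at 6 months.

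SAP 3.3 lists DR as a secondary endpoint. SAP 8.7 makes no multiplicity adjustment for secondary analyses apart from the sequential survival analyses. Neither document says that the responder comparison is non-randomized, and neither gives an all-randomized counterpart to DR.

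For time to response, SAP 6.2.3 says: "Time to response will be analyzed according to the Kaplan-Meier method and compared between treatment groups using the log-rank test". It names no population. The matching shells (11.3.4.2.12, 11.3.4.2.13, 11.3.4.3.11 and 11.3.4.3.12) print only medians with 95% CIs.

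**The concern.** Randomization makes the arms comparable at baseline. It does not make the responders in one arm comparable with the responders in the other. If the combination brings in patients who would not have responded to dexamethasone alone, Arm A's responders are a wider group and may on average have a worse prognosis than Arm B's few. A hazard ratio between these groups mixes any effect on durability with the difference in who was selected.

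At stake is how a named secondary endpoint is read. An unlabelled p-value near 0.05, or a hazard ratio on either side of 1, could be cited for or against durable benefit when it supports neither reading.

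**Working it through.** **The plan's own figures.** The documents give no calculation for the DR comparison, so I checked the figures that they do give.

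- PFS events, Schoenfeld formula with 2:1 allocation: (1.960 + 1.282)² / [(2/3)(1/3)(ln 0.625)²] = 10.507 / 0.04909 = 214.05, rounded up to 215. The plan says about 210, which gives power 0.894 against the stated 90%. This agrees.
- Exact 95% CI for 12 of 40 responses: 16.6% to 46.5%, as stated.

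**Inputs for the illustration.**

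- From the documents: 167 and 83 patients; control median PFS of 12 weeks (one of the examples in Protocol 10.1); target hazard ratio 0.625; Arm A response 30% (the futility threshold).
- Assumed: Arm B response 10% (5% also tried); response at week 8; follow-up 104 weeks; a prognostic score Z with log-hazard SD γ of 0.5 or 0.8; correlation ρ of 0.5, 0.8 or 1.0 between Z and the tendency to respond.

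**Number of responders.** Arm A: 167 × 0.30 = 50.1. Arm B: 83 × 0.10 = 8.3. With no selection at all (γ = 0) and a hazard ratio of 0.625, the log-rank test in these responders reaches two-sided p < 0.05 in favour of Arm A in 29% of simulated trials.

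**Model 1.** Time to progression T is exponential with hazard h₀·exp(−γZ)·HR^arm. A responder has T > 8 weeks and ρZ + √(1−ρ²)·e (e an independent standard normal) above an arm-specific cut that gives the stated response rate. DR = T − 8, censored at week 104. Hazard ratios come from a Cox model with 300,000 patients per arm. At 30% vs 10% response:

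| γ | ρ | DR HR, no effect on T (PFS HR 1.00) | DR HR, conditional HR 0.55 | PFS HR, conditional HR 0.55 |
|---|---|---|---|---|
| 0.5 | 0.5 | 1.15 | 0.68 | 0.60 |
| 0.5 | 0.8 | 1.26 | 0.72 | 0.60 |
| 0.5 | 1.0 | 1.35 | 0.74 | 0.60 |
| 0.8 | 0.5 | 1.20 | 0.76 | 0.65 |
| 0.8 | 0.8 | 1.39 | 0.84 | 0.65 |
| 0.8 | 1.0 | 1.61 | 0.89 | 0.65 |

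Other settings:

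- 20% vs 10% response: DR HR 1.08 to 1.34 with no effect on T, and 0.64 to 0.74 under benefit.
- 30% vs 5% response: 1.23 to 2.05 with no effect, and 0.72 to 1.17 under benefit. Under benefit it clearly exceeds 1 only at γ = 0.8 with ρ = 1.0; at γ = 0.8 with ρ = 0.8 it is about 1.0.
- γ = 0: the DR HR equals the true hazard ratio, so there is no bias.

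**Model 2, built differently.** Patients who would respond on either arm have a median DR of 8 months in both arms. Patients who respond only because of the drug have a median DR of 3 to 6 months (assumed). Response is 30% vs 10%, the cut-off is 24 months, and each scenario has about 1,000 trials of 167 vs 83. The responder-only HR runs from 1.66 (3 months) to 1.17 (6 months), against Arm A. Over all randomized patients, with non-responders counted as zero, mean time in response is 1.88 to 2.61 months in Arm A and about 1.0 in Arm B. If the drug also lengthens DR in those who respond on either arm (12.8 vs 8 months, HR 0.625), the responder-only HR is 1.39 when drug-induced responses have a median of 3 months and 0.99 at 6 months. With 20% response in Arm B it is 0.79 to 0.91.

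**The case against.** **Impact is limited, and this stands.** The objective is to assess DR and to compare PFS. PFS, survival and response rate are all compared in all randomized patients, and no claim is tied to the DR p-value. Four of the six tables came in with SAP version 5.0, whose added analyses are called supportive. The two main tables, 11.3.4.4.1 and 11.3.4.4.2, carry no such label.

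**Most inputs are assumed, and this stands.** Arm B response, prognostic spread, correlation, response time and follow-up are not in the documents. The no-effect scenario is also somewhat artificial: response is a fall in M-protein and progression is a rise from its lowest value, so the two are linked.

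Four stronger readings are tempting and are not supported:

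- **That the analysis would reverse a real benefit.** In Model 1 at 30% vs 10%, the hazard ratio under benefit stays below 1 in every setting. Reversal needs 5% control response with the strongest spread and perfect correlation or, in Model 2, drug-induced responses far shorter than the rest.
- **That a calculable share of the treatment effect is lost.** PFS runs from randomization and DR from first response. They are different quantities, so the gap between their hazard ratios is not all lost effect.
- **That a Cox model is specified for DR.** SAP 6.2.3 names only the log-rank test. Cox regression is named for PFS, and for DR it can only be inferred from the hazard ratio in the shells.
- **That time to response has the same fault.** Its population is not stated and its shells print no p-value or hazard ratio.

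Custom supports showing DR curves and medians in responders. It does not support an unlabelled between-arm test.

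**Conclusion.** The point holds. The DR comparison is made in groups selected by a post-randomization outcome, so its p-value and hazard ratio are not estimates of the drug's effect on durability. That conclusion follows from the definitions and needs no simulation.

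The sizes are illustrative. At 30% vs 10% response, with response related to prognosis, the responder-only hazard ratio is about 1.2 to 1.6 when nobody's time to progression changes, and about 0.7 to 0.9 when the all-patient PFS hazard ratio is 0.60 to 0.65. In Model 1 the distortion disappears if response is unrelated to prognosis. Size and direction in this trial cannot be known from the documents. With about 8 Arm B responders, the test would be weak even without selection.

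The matter should be corrected, but it concerns a secondary endpoint only. The primary PFS analysis and its sample size are untouched.

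**What to change.** 1. In SAP 6.2.3 and Protocol 10.2.3.3, make DR in responders descriptive by arm: Kaplan-Meier curve, median, 95% CI and 6-month estimate.
2. In Tables 11.3.4.4.1 to 11.3.4.4.6, remove the between-arm p-values and hazard ratio, or label them descriptive and non-randomized. Give the 6-month difference the same label.
3. Add one supportive comparison in All Randomized Patients, such as mean time in response to a fixed horizon (for example 12 months) with non-responders counted as zero. This is the area between the Kaplan-Meier curve for PFS and the curve for first response or PFS event, with a bootstrap CI. It mixes response rate with durability, so it supplements DR and does not replace it. This SAP version follows a June 2017 regulatory meeting, and the Protocol 5.11 note already treats the PFS endpoint as met. If the measure is added after the data were seen, call it post hoc.
4. For time to response, name the population. If a log-rank test is run, run it in All Randomized Patients and not in responders only. The current shells need no deletion.

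The cost is SAP and protocol wording, edits to six shells and a little programming, with no new data. Because four of the shells came in with an amendment that followed regulator meetings, the relabelling should be explained there. The downside is that the familiar DR p-value and hazard ratio no longer serve as inferential results.

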10 STATISTICAL METHODS

10.1 SAMPLE SIZE

- 1. Arm A (plitidepsin plus dexamethasone combination): approximately 167 patients.
- 2. Arm B (dexamethasone single agent): approximately 83 patients.

The number of patients randomized in the trial has been calculated based on PFS estimates obtained from the previous phase II study (APL-B-014-03).

Approximately 210 progression or death events would be needed in this trial to detect a HR of 0.625 in favor of the combination arm (equivalent to an increase of 60% in PFS, i.e., from 10 to 16 weeks, from 12 to 19.2 weeks, from 16 to 25.6 weeks, etc.) with 90% power and 1-sided 2.5% significance level. As a preliminary hypothesis, it is estimated that up to 250 randomized patients will be needed to achieve the 210 events in 24-30 months.

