6.2.3 Secondary analyses

Overall survival:

Although the study is powered for the evaluation of the main endpoint PFS, two analyses of OS will be performed to ascertain if a trend in OS is observed in favor of the experimental arm. A first analysis of OS will be performed concomitantly with the final PFS analysis. In addition, a second analysis of OS will be performed when 80% death events (approximately 200 death events) have occurred or 24 months after the inclusion of the last patient, whichever occurs first. At the interim OS analysis the significance level determined by the O'Brien-Fleming boundary with overall 2.5% 1-sided significance level will be used.

OS analyses will be performed according to the Kaplan-Meier method and the unstratified and stratified log rank tests will be used in order to ascertain if clinically significant OS effect in favor of the experimental arm is observed.

It is anticipated that an indeterminate number of patients in the control arm will switch treatment after progression to plitidepsin plus dexamethasone. This could cause the size of the effect on OS to be difficult to interpret. Consequently, if the OS results show to be substantially influenced by crossover, the Sponsor will study the estimated effect of crossover in a first sensitivity analysis excluding the patients who crossed over and a second analysis censoring survival at the time of crossover. Estimates of the unbiased effect in survival will be studied by means of, rank preserving structural failure time (RPSFT)

models for correcting for treatment changes (2), by the inverse probability of censoring weighting (IPCW) method (6) and by means of the two-stage method proposed by Latimer *et al.* (7) in order to try to control any bias caused by treatment crossover.

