8.7 Subgroup analyses

Analysis of efficacy profile by age in order to characterize a potential benefit of the drug in elderly population is planned. Exploratory efficacy subgroup analyses according to genetic risk, the refractory status to prior therapies such as bortezomib, lenalidomide/thalidomide, last prior therapy, IMiD therapy and PIs are planned. No other specific subgroup analysis is planned for efficacy. However, the influence of the study strata and other prognostic factors on the efficacy endpoints will be studied in the multivariate analysis.

No formal statistical allowance will be made for multiple subgroup investigations, but any apparent subgroup interactions will be interpreted appropriately in a cautious way.

Analysis of safety profile by age, gender and body mass index (BMI) will be provided as specified in section 12.7.

Handling of multicenter data

No randomization or stratification by center will be performed as the sample size by center is expected to be low. Further “by center” analyses may be performed upon request if appropriate.

Handling of multiple comparisons

Single comparison of PFS between arm A and B will be made for the primary endpoint. No adjustment, except for the sequential OS analyses described in section 5.1, will be made for multiple comparisons in secondary analyses.

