11.3.4.5 Analysis of crossover

Table 11.3.4.5.1 RR to combination treatment in patients who crossed over from Arm B to Arm A (“All Crossover Patients” population)

		After crossover (N,%)							
		sCR	CR	VGPR	PR	MR	SD	PD	NE
Before crossover	sCR								
	CR								
	VGPR								
	PR								
	MR								
	SD								
	PD								
	NE								

Table 11.3.4.5.2 Inpatient PFS comparison of patients who crossed over from Arm B to Arm A (“All Crossover Patients” population)

PFS	Before crossover	After crossover
Median		
PFS at 6 months		

Table 11.3.4.5.3 PFS comparison of patients (“All Randomized Patients” population)

PFS	Arm A	Arm B	
		Before crossover	After crossover
Median			
PFS at 6 months			

Listing 11.3.4.5.4 Best response and PFS before and after crossover.

Patient id.	Cycle of crossover	Best response		PFS	
		Before crossover	After crossover	Before crossover	After crossover
...					

Listing 11.3.4.5.5 Best response and PFS before in crossover patients.

Patient id.	Independent review assessment				Investigator assessment			
	Best response	PFS	PFS event	PD confirmation	Best response	PFS	PFS event	PD confirmation
...								

Table 11.3.4.5.6 Time to crossover

	N	Median	Min	Max
Time to crossover (months)				

Table 11.3.4.5.7 Baseline characteristics comparison patients without crossover vs crossover

Variable**	Value	N	Without Crossover	Crossover	p-value*
Sex	F	XXX	XX (XX.X%)	XX (XX.X%)	X.XXXX
	M	XXX	XX (XX.X%)	XX (XX.X%)	
Age	Median(range)	XXX	XX.X (XX-XX)	XX.X (XX-XX)	X.XXXX
...					

(*)Fisher's exact test (categorical variables); Mann-Whitney-Wilcoxon (continuous variables)

(**)Sex, age, PS (ECOG), BSA, Durie Salmon stage, International Staging System, Secretary/Non-secretory, MM type, time from diagnosis, time from last PD, number of prior lines, status to prior therapy, status to prior bortezomib therapy, status to prior thalidomide/lenalidomide therapy, status to prior IMiD therapy, status to prior PIs therapy, stem cell transplantation, plasma cells, hemoglobin, creatinine, calcium, genetic risk, lytic lesions and plasmacytomas.

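### The crossover versus no-crossover baseline table cannot rule out a better prognosis in crossover patients: it gives only unadjusted difference-test p-values within about 83 Arm B patients

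*SAP*

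**What the plan says.** SAP 6.2.3, under the analysis of crossover, states that the baseline comparison "will be done to rule out that patients with crossover can have a better prognosis than patients without crossover". The output is Table 11.3.4.5.7, "Baseline characteristics comparison patients without crossover vs crossover". It has a count and percentage or a median and range per group, plus a p-value column. The footnote names the tests as Fisher's "exact test (categorical variables); Mann-Whitney-Wilcoxon (continuous variables") and lists 24 variables. No difference, confidence interval, margin or significance threshold appears.

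The crossover set is "all patients randomized to Arm B who have documented disease progression after their eighth week from randomization and cross over to Arm A" (SAP 4.1). The SAP anticipates that "an indeterminate number of patients in the control arm will switch treatment after progression" (6.2.3). Protocol 10.1 plans "Arm B (dexamethasone single agent): approximately 83 patients". SAP 8.7 says that no adjustment, apart from the one for the sequential OS analyses, "will be made for multiple comparisons in secondary analyses".

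For the two-stage method, SAP 6.2.3 adds a stepwise logistic regression and a PFS comparison of the same two groups. These are reported in Tables 11.3.4.1.13 and 11.3.4.1.14.

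**The concern.** A difference test asks whether the data contradict equality. A non-significant result does not show that a relevant difference is absent, least of all in small groups. To rule something out, one needs an interval narrow enough to exclude it. The stated purpose and the planned output therefore do not match.

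Selection is a live issue here. Crossover requires progression at least eight weeks after randomization, so early deaths fall into the no-crossover group, but so do patients who never progress. The SAP's own revision history (v4.0 to v5.0) records the hypothesis that patients without crossover or later therapy could have a worse prognosis.

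Two of the planned OS analyses depend directly on comparable groups: the one that excludes switchers and the one that censors at the switch. The two-stage method also needs no unmeasured confounding at progression. As laid out, its Weibull table (11.3.4.1.15) shows only intercept, treatment arm, scale and shape, with no prognostic covariates.

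**Working it through.** **Inputs from the documents.** Hazard ratio 0.625, 90% power, one-sided 2.5%, about 210 events, 250 patients and about 83 in Arm B (Protocol 10.1); 2:1 allocation (Protocol 5.10); 255 patients randomized in the end (note in Protocol 10.2.3.4); tests and 24 variables (SAP Table 11.3.4.5.7).

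**Assumptions not in the documents.** A relevant imbalance of 0.5 SD, a two-sided 5% threshold, normal data, and a no-crossover group drawn from Arm B only. The number of switchers is unknown, so a range of splits is shown.

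**1. The plan's own figure.** The trial is sized to "detect a HR of 0.625 in favor of the combination arm". Schoenfeld's formula gives (1.960 + 1.282)² / [(2/3)(1/3)(ln 0.625)²] = 10.51 / 0.0491, or 215 events after rounding up, close to the stated 210 (power at 210 events is 89.4%). One third of 250 is 83.3, which agrees with the planned Arm B. The plan gives no power or precision figure for the crossover comparison.

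**2. Precision.** In SD units the 95% half-width is 1.96 × √(1/m + 1/n), smallest when the groups are as equal as possible.
- 41 versus 42: 1.96 × 0.2195 = 0.43 SD.
- 20 versus 63: 1.96 × 0.2567 = 0.50 SD.
- 42 versus 43 (Arm B of 85, one third of 255): 1.96 × 0.2169 = 0.43 SD.

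**3. Chance of missing a 0.5-SD imbalance.** At 41/42 the normal approximation gives power Φ(0.5/0.2195 − 1.96) = Φ(0.318) = 62.5%, a miss rate of 37.5%. The noncentral t gives 38.6%. Simulating the test that the SAP names gives:

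| Crossover / no crossover | Mann-Whitney miss rate |
|---|---|
| 42 / 43 (85 patients) | 39.9% |
| 41 / 42 | 40.8% |
| 37 / 46 | about 41.5% |
| 33 / 50 | about 43% |
| 28 / 55 | about 46% |
| 21 / 62 | about 52% |
| 17 / 66 | about 58% |

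The miss rate depends on the size of the smaller group, whichever group that is. For a categorical factor at 41/42, Fisher's test misses 30% versus 50% in 57% of trials.

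**4. The opposite error.** With identical groups and 24 independent tests at 5%, the chance of at least one p < 0.05 is 1 − 0.95²⁴ = 71%. The variables overlap (for example bortezomib status with proteasome inhibitor status, and secretory status with myeloma type), so 71% is only an illustration.

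**5. Sensitivity of the miss rate.** At 41/42 it is 43% for uniform data and 21% for log-normal data (log-scale SD 0.5). With a threshold of 0.10 it is 29% at 41/42 and 32% at 30/53. If Arm A were counted in the no-crossover group, the normal approximation gives 17% (41 versus 209) to 43% (20 versus 230), but most of that group could never have crossed over.

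**The case against.** The SAP sets no decision rule for this table, so reliance on non-significance is an inference. Group summaries are printed, so a reader can see the size of any imbalance. That stands in part: the p-value is still the table's only inferential output, and the stated aim is to rule something out.

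The SAP's comparison of these groups is also wider than one table. Table 11.3.4.1.13 gives odds ratios with 95% limits, and Table 11.3.4.1.14 gives a hazard ratio with its interval. The lack of effect sizes and intervals therefore applies to Table 11.3.4.5.7, not to the whole plan. Neither of the other two tables has a margin.

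A reader might infer that every crossover-related reading of OS rests on this comparison. The documents do not support that. The rank preserving structural failure time (RPSFT) model does not depend on switchers and non-switchers being alike. Inverse probability of censoring weighting (IPCW) adjusts for a long list of baseline and time-dependent covariates. No OS analysis is made conditional on Table 11.3.4.5.7, and the revision history calls these additions supportive.

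A reader might also take the roughly 40% miss rate as a fixed lower bound. It is not: it changes with the distribution and the threshold, and it applies to each variable separately.

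**Conclusion.** The point holds as a minor one. A better prognosis in crossover patients cannot be ruled out at this sample size. The 95% half-width is at least about 0.43 SD in an Arm B of about 83, whatever the split. Given a 0.5-SD imbalance, two-sided 5% and normal data, the named test misses it in about 40% of trials at best and in over half at 21/62. The precision result does not depend on the assumed imbalance or on a testing threshold. The miss rates do.

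The consequence is limited to the OS analyses that exclude switchers or censor at the switch, and to the two-stage method. It would go too far to infer that a given distortion of the Arm A versus Arm B hazard ratio follows. The documents give neither the number of switchers nor the prognostic strength of the factors, so no such size has been calculated.

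**What to change.** - In SAP 6.2.3, replace *to rule out* with *to describe*.
- In Table 11.3.4.5.7, report standardized differences with 95% confidence intervals, instead of the p-values or beside them.
- Define the comparison group as Arm B patients with Investigator-documented progression at eight weeks or later, that is, those who could have crossed over.
- State that non-significant p-values will not be taken as evidence of comparable prognosis, and that the exclusion, censoring and two-stage analyses are read as potentially confounded.

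An equivalence margin should not be added. A margin of ±0.25 SD, for example, is 0.50 SD wide, while the narrowest interval is about 2 × 0.43 = 0.86 SD wide, so it could never be met.

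The cost is some SAP wording and one changed table column, with no new data. Restricting the group widens the intervals further, and the sponsor gives up a reassuring statement about a supportive analysis.
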